7.1.2 Definitions and Derivations

Baseline

Unless otherwise specified, baseline is defined as the last available value prior to the prime immunization.

> Conversion among day, month and year

Month = day/30.4375, and year = day/365.25, rounded to a decimal place.

Study Day

Taking the date of first dosing as the start date,

- \checkmark If study date < date of first dosing, then study day = study date date of first dosing
- \checkmark If study date >= date of first dosing, then study day = study date date of first dosing + 1

Adverse Events Times

Occurrence time of AE (day) = AE onset date – the corresponding immunization date.

Duration of AE = end date of AE - AE onset date + 1.

Treatment Emergent Adverse Event (TEAE)

Treatment Emergent Adverse Event (TEAE), which is defined as any AE with an onset after the first immunization (if the AE was absent before the first immunization) or worsened after the first immunization (if the AE was present before the first immunization). The implementation of TEAE complies with the following rules: AE with missing start time or AE occurs after or on the day of the prime immunization will be regarded as TEAE, and otherwise will be regarded as non-TEAE.

> The Severity of related TEAE

If the severity of related TEAE under China NMPA Guidance is at least grade 1, which under FDA Guidance is less than grade 1 (ie. NULL in EDC), the corresponding event will not be regarded as adverse event under FDA Guidance.

Similarly, if the severity of related TEAE under FDA Guidance is at least grade 1, which under China NMPA Guidance is less than grade 1 (ie. NULL in EDC), the corresponding event will not be regarded as adverse event under China NMPA Guidance.

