#### AE excludes:

- Medical or surgical procedures, such as operation, endoscopy, tooth extraction, infusion (the
  operation should not be collected as AE, but the diseases leading to these operations should
  be reported as AE);
- Existing diseases or conditions that exist or have been detected but have not worsened prior to the start of using the study drug, including abnormal results of laboratory tests.
- Transitory effects on laboratory tests due to the known mechanism of action of the drug, where there is no manifest clinical risk or evidence of potential lasting harm, judged by the investigator.

Treatment-emergent AE (TEAE) is defined as any AE with an onset date on or after the first administration of IMP (if the AE was absent before the first vaccination of IMP) or worsened after the first vaccination of IMP (if the AE was present before the first administration of IMP). AEs with an onset date more than 28 d after the last vaccination of IMP will be considered as treatment emergent only if assessed as related to IMP by the investigator.

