# 13.1.4 Primary endpoints

All AEs will be coded using the most recent version of Medical Dictionary for Regulatory Activities (MedDRA version 23.0) coding system to get a system organ class (SOC) and preferred term (PT) for each AE.

AEs and solicited reactions will be summarized using the Safety Set. In general, safety parameters will be analyzed by grouping and for each immunization, i.e., for:

- Day 1-21 (pre-boost)
- Day 21(post-boost) 28

Additionally, AEs and reactions will be summarized for all dose levels combined for each type.

For each analysis, the number and percentage of subjects reporting at least one AE will be summarized by PT nested within SOC for each of the following AE types using the Safety Set:

- Any AE
- Related AE
- >Grade 3 AE
- Related AE >Grade 3
- AE leading to withdrawal
- Any SAE
- Related SAE

Moreover, the number and percentage of subjects with any AE will be summarized by worst grade by PT nested within SOC.

During 14 days post vaccination (including the day of BNT162b1/placebo vaccination), evaluate reactogenicity by daily solicited reactions, including local reactions (vaccination site: pain/tenderness, erythema/redness, induration/swelling) and systemic reactions (nausea, vomiting, diarrhea, headache, fatigue, myalgia, arthralgia, chills, loss of appetite, malaise, and fever), as well as non solicited AE. In addition, body temperature (axillary) was collected as the indicator of reactogenicity (fever was defined as axillary temperature ≥37.3 °C or oral temperature ≥38 °C).

For each solicited reaction (including fever), the percentage of subjects will be aggregated according to the severity of the events and the total number of subjects within 14 days of each vaccination/placebo.

Local and systemic responses were recruited within 14 days after each vaccination, non-solicited TEAE within 21 days after the prime vaccination and 28 days after boost vaccination, and IMP-

related AE were studied after 28 days. Adverse reaction classification criteria given in appendix B and appendix C were used for classification. During the study period, AEs uninvolved in the appendix grading scales will be graded clinically by the investigator according to the criteria in Section 10.3.1.

For each immunization, the number and percentage of subjects reporting at least one local reaction or systemic reaction will be summarized for each of the following types using the Safety Set:

- Any local reactions or systemic reactions

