2.2 Purpose of Analyses

The purposes of the planned analyses described in this SAP are to assess the safety and tolerability profile, immunogenicity of prime/boost (P/B) immunization given 21 days apart from different dosages in SARS-CoV-2 naïve Chinese healthy population through 28 days after boost vaccination. Results from the analyses will be included in the final Statistical Analysis Report and Clinical Study Report and also be utilized for regulatory submissions, manuscripts, or other clinical development activities.

Post-hoc exploratory analyses not identified in this SAP may be performed to further examine the study data. These analyses will be clearly identified, where appropriate, in the final clinical study report. Additional analyses not prospectively identified in this SAP may also be performed for publications, regulatory or funding inquiries. These analyses, if performed, may not be reported in the final clinical study report, but will be fully documented in the document containing these additional analyses.

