2.3 Summary of Statistical Analysis Changes to the Protocol

The analyses described in this analysis plan are consistent with the analyses described in the study protocol.

3 Objectives

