7.5 Exploratory analyses

7.6 Safety Analyses

7.6.1 Adverse Events

All AEs will be coded using the recent version of MedDRA Version 23.0, and be summarized by SOC and PT. Additionally, solicited AEs, including systematic AEs and local AEs predefined in the protocol, will be summarized. The severity of AEs will be analyzed under China NMPA Guidance (Refer to Appendix B in the protocol: *NMPA Guidance for Adverse Events Grading Scale for Preventive Vaccine Clinical Trials in China*), and that of adverse reactions will also be analyzed under US Food and Drug Administration (FDA) Guidance (Refer to Appedix C in the protocol: *FDA Toxicity Grading Scale in Preventive Vaccine Clinical Trials*) in addition to China NMPA guidance.

This study is mainly to analyze Treatment Emergent Adverse Events (TEAEs), which are defined as any AEs with an onset on or after the first immunization (if the AE was absent before the first immunization) or worsened after the first immunization (if the AE was present before the first immunization). The Non-TEAEs occur before the first immunization will not be included in the analysis, but will be listed. Unless particularly stated, AEs mentioned in below text are TEAEs.

All solicited AEs, including systematic and local AEs, will be graded based on the criteria given in "NMPA Guidance for Adverse Events Grading Scale for Preventive Vaccine Clinical Trials in China". And all related systematic and local reactions will be graded at the same time according to "US FDA Guidance for Industry. Toxicity Grading Scale for Healthy Adult and Adolescent Volunteers Enrolled in Preventive Vaccine Clinical Trials". The solicited systematic and local reactions will be analyzed based on both NMPA and US FDA guidance.

The episodes of AEs, number and percentages of subjects who experience at least one TEAE as follows will be presented by group:

- Overall Summary of Adverse Events
- > Any TEAEs by SOC and PT
- Related TEAEs by SOC and PT
- Unrelated TEAEs by SOC and PT
- > Any TEAEs by Solicited and Unsolicited AEs
- Related TEAEs by Solicited and Unsolicited AEs
- Unrelated TEAEs by Solicited and Unsolicited AEs
- ➢ Grade≥3 TEAEs by SOC and PT, according to China NMPA guidance

- ➢ Grade≥3 related TEAEs by SOC and PT, according to China NMPA guidance
- ➢ Grade≥3 Solicited Systematic and Local Reactions, according to China NMPA guidance
- ➢ Grade≥3 Solicited Systematic and Local Reactions, according to US FDA guidance

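### The SAP's TEAE rule omits the protocol's 28-day relatedness limit, and its implementation step leaves out worsened AEs, while the SAP declares no change from the protocol

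*SAP*

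**What the plan says.** **Protocol.** Section 10.1.1 defines a TEAE by onset on or after the first dose, or worsening after it. It then adds a limit: an event starting more than 28 days after the last vaccination "will be considered as treatment emergent only if assessed as related to IMP by the investigator". Section 13.1.4 follows the same logic. Its analysis windows are per immunization (the first is "Day 1-21 (pre-boost"), and for the later period it says that IMP-"related AE were studied after 28 days". The safety analysis paragraph of the Trial Summary asks for AE summaries that cover aggravation after vaccination.

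**SAP.** Section 7.1.2 defines TEAEs to include any AE that "worsened after the first immunization (if the AE was present before the first immunization". Its next sentence gives the rule to be programmed: "AE with missing start time or AE occurs after or on the day of the prime immunization will be regarded as TEAE", with all other events non-TEAE. Section 7.6.1 restates the definition, says that AE means TEAE unless stated otherwise, and adds: "The Non-TEAEs occur before the first immunization will not be included in the analysis, but will be listed". None of these statements has a 28-day or relatedness condition. Section 2.3 says: "The analyses described in this analysis plan are consistent with the analyses described in the study protocol".

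**Timing.** SAP 2.2 frames the purpose as safety and immunogenicity "through 28 days after boost vaccination", but SAP 3.2 includes safety to the end of the study and SAP 7.10 schedules updates at Months 6 and 12.

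**Unblinding.** Protocol 8.3 and SAP 4.2.1 keep subjects, research staff and the sponsor's study managers blinded for the whole trial. Protocol 8.5, the Trial Summary, SAP 4.2.2 and SAP 7.10 place unblinding at the Day 50 analysis, and Protocol 13.2 places it after that analysis. These sections exempt only the subjects, and none names who receives the codes.

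**The concern.** Almost every AE table in SAP 7.6.1 rests on the TEAE definition, so an undeclared change to it runs through the whole set. A programmer working from Protocol 10.1.1 and one working from SAP 7.1.2 would produce different Month 6 and Month 12 tables from the same data, and SAP 2.3 would tell the reader that no difference exists.

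The second fault lies inside SAP 7.1.2. The definition admits worsened pre-existing events, but the rule meant to implement it has no worsening test. Unlike the missing limit, this can alter the related-TEAE tables as well.

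The unblinding question is secondary. It bears on the late secondary endpoint of vaccine-associated AEs to Months 3, 6 and 12 (Protocol 5.2.2), which depends on investigators' causality judgements.

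**Working it through.** **1. The plan's own TEAE figure.** Protocol 13.3 and SAP 4.3 give 86.5% for at least one TEAE among 24 subjects at a rate of 8%. Check: 1 − 0.92^24 = 0.8648, so it reproduces. The 8% is an assumed rate, so neither version of the rule changes this figure.

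**2. The rules side by side.**

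| Event | Protocol 10.1.1 | SAP definition | SAP implementation rule |
|---|---|---|---|
| Onset on or after prime, up to 28 days after last dose | TEAE | TEAE | TEAE |
| Onset more than 28 days after last dose, related | TEAE | TEAE | TEAE |
| Onset more than 28 days after last dose, unrelated | not a TEAE | TEAE | TEAE |
| Present before prime, worsened after, original start date kept | TEAE | TEAE | non-TEAE |
| Same, but worsening entered as a new post-dose record | TEAE | TEAE | TEAE |

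Row 3 is the undeclared difference between the documents. Row 4 is the SAP's conflict with itself. The 28-day limit does not affect related-TEAE tables; row 4 can.

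**3. When the limit begins to matter.** The last day on which relatedness is ignored is 22 + 28 = Day 50 for a boost on Day 22. With the ±2-day boost window it is 20 + 28 = Day 48 to 24 + 28 = Day 52. For a subject who receives only the prime dose it is 1 + 28 = Day 29. Visit 9 is Day 50 ± 4. The Day 50 analysis is therefore barely touched, apart from prime-only subjects and a few days of window slack. Under the SAP the period has no end: to the nominal Month 12 visit that adds 366 − 50 = 316 days, and 316/366 = 86% of follow-up.

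**4. Which late unrelated events reach the database.** Protocol 10.2.2 collects AEs leading to withdrawal or discontinuation throughout, and otherwise only related events after 28 days post-boost. Protocol 10.2.3 covers SAEs whatever their cause. Table 2 also has an AE-recording row at Visits 10–12 with no stated restriction. The tables affected are any TEAE, unrelated TEAE, TEAE leading to discontinuation, and treatment-emergent SAE.

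**5. Size of one event** (exact Clopper-Pearson 95% CI, the method in SAP 7.1.1).
- Arm of 24: 0/24 = 0% (0–14.2%) becomes 1/24 = 4.2% (0.1–21.1%).
- Arm pooled over both age groups: 1/48 = 2.1% (0.05–11.1%).

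**6. How often it might happen.** The documents give no rate, so the yearly rates y below are assumptions. The probability per subject over 316 days is q = 1 − (1 − y)^(316/365.25), and the chance of at least one event in 24 is 1 − (1 − q)^24.

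| Assumed yearly rate | q | At least one in 24 | Expected among 144 |
|---|---|---|---|
| 1% | 0.87% | 18.8% | 1.25 |
| 2% | 1.73% | 34.3% | 2.50 |
| 5% | 4.34% | 65.5% | 6.25 |
| 10% | 8.71% | 88.8% | 12.55 |

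**7. Unblinding passages.** Protocol 8.4 confines unblinded reports to unblinded personnel and lists investigators and trial statisticians as blinded. Protocol 8.5 bars the investigator from breaking the blind except for medical need. The people identified as unblinded (dispensers and vaccination nurses; the IDMC for significant events) are not linked to the Day 50 analysis.

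**The case against.** Several points on the other side carry weight.

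- **Worsened events may never be lost.** Protocol 9.1.2 and the Table 2 footnotes class occurrences before the prime dose as medical history, and Protocol 10.1.1 counts deterioration from baseline as an AE. A worsening could then be a new record with a post-dose date, which the SAP rule counts correctly. This stands as a limit on impact. It does not remove the conflict: Table 2 also records AEs at screening and before prime, and no section fixes the eCRF convention.
- **The unlimited rule suits the SAE endpoint.** Protocol 5.2.2 asks for SAEs to Month 12 without a causality limit. A reader might infer that late unrelated SAEs in the tables are themselves a harm; the documents say the opposite. The fault is the undeclared difference.
- **Windows already do much of the limiting.** Protocol 13.1.4 lists its tables as AEs rather than TEAEs and works by dose window. SAP 7.1.2 dates AEs from the corresponding immunization, and SAP 7.6.1 reports by dose and by occurrence. But the by-dose summary has no 28-day end, the occurrence categories are not given, and the table shells are in a separate attachment not seen here.
- **Little rests on these tables.** The primary endpoints end by 28 days post-boost, the late AE endpoint covers related events only, and SAP 7.1 plans no formal testing. All of this stands.

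A reader might also infer that the vaccine–placebo contrast in any TEAE would shrink noticeably. Taking the foreign placebo injection-site pain rate in Protocol 4.2.4.1 (2/9 = 22.2%) as a stand-in, and assuming that 1%, 5% or 20% of subjects have a late unrelated event independently of earlier ones, the expected rise on placebo is 77.8% × 0.01 = 0.8, × 0.05 = 3.9 or × 0.20 = 15.6 points. These are expected values under assumed rates, not maxima. The 22.2% is one symptom after one dose in nine subjects, and 20% presumes collection beyond Protocol 10.2.2. The documents do not support a claim of material distortion.

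Nor do they show that investigators will be unblinded at Day 50: Protocol 8.3, 8.4 and 8.5 lean the other way.

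**Conclusion.** The TEAE rule in the SAP is wrong as written on two counts. It drops the protocol's 28-day relatedness limit while SAP 2.3 declares consistency, and its implementation sentence omits worsened pre-existing events that its own definition and the protocol's Trial Summary include.

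The consequence is confined mainly to descriptive Month 6 and 12 tables. One late unrelated event changes a cell by 4.2 points in an arm of 24, or 2.1 points in a pooled arm of 48. The number of such events cannot be derived from the documents and is likely small if collection follows Protocol 10.2.2. The worsened-event conflict changes counts only if a worsening keeps its pre-dose start date, which nothing in the documents rules out. It would be too strong to say that the primary safety results or the Day 50 analysis are compromised.

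The unblinding passages are ambiguous rather than shown to be wrong. They need reconciling, and the size of any assessment bias cannot be estimated.

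**What to change.** 1. **28-day limit.** Add the relatedness limit to SAP 7.1.2 and 7.6.1, or state and justify the difference in SAP 2.3. If the limit is added, report all-cause SAEs to Month 12 without the TEAE filter, since Protocol 5.2.2 requires them and the SAP's by-group SAE tables cover only treatment-emergent ones.
2. **Worsened events.** Add to the implementation rule in SAP 7.1.2 that an AE with onset before the prime dose that worsened after the first immunization is a TEAE, dated from the worsening.
3. **Windows.** Tabulate the 21-day post-prime and 28-day post-boost windows of Protocol 13.1.4 separately from later events.
4. **Unblinding (clarification).** Reconcile Protocol 8.3 and SAP 4.2.1 with the Trial Summary, Protocol 8.5 and 13.2, and SAP 4.2.2 and 7.10. Name the roles that receive codes at the Day 50 analysis, and settle whether this happens at or after it. Keep site investigators and causality assessors blinded for the whole trial, as Protocol 8.3 already implies, and leave the emergency, pregnancy and IDMC provisions unchanged.

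The cost is a few sentences in the SAP and protocol, one window split in the AE tables and, if the limit is restored, one extra SAE table. No new data are needed. Because Protocol 8.4 already restricts unblinded reports, no new firewall is needed either; the drawback is that investigators do not see individual allocations while follow-up continues.

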## 4.2.4.1 Safety summary

According to the periodic summary of the United States Phase I/II clinical study, pain at the injection site was the most common local reaction within 7 days of the first dose and the second

dose of vaccine; after the first vaccination, probability of pain in 10  $\mu g$  group was 58.3% (7/12), in 30  $\mu g$  group and 100  $\mu g$  group were 100.0% (12/12), and in placebo group was 22.2% (2/9). After the second vaccination, there were 83.3% and 100.0% of subjects got pain respectively in the dose level of 10  $\mu g$  and 30  $\mu g$ , while 16.7% subjects in placebo group got pain. All local reactions were mild or moderate except the 100  $\mu g$  group reported severe pain after inoculation of BNT162b1.

Within 7 days of each vaccination, the most common systemic events reported in BNT162b1 and placebo groups were mild to moderate fatigue and headache. Fatigue and headache were more common in BNT162b1 than that in placebo group. Furthermore, chills, muscle pain and joint pain were reported in the BNT162b1 group, but not in the placebo group. Systemic events increased with dose levels, and there were an increased number of subjects reporting systemic events after the second vaccination (10  $\mu$ g and 30  $\mu$ g groups). After the first vaccination, there were 8.3% (1/12) of subjects respectively in 10  $\mu$ g group and 30  $\mu$ g group, and 50.0% (6/12) of subjects in 100  $\mu$ g group got fever (defined as  $\geq$ 38.0° C). Based on the reactogenicity reported after the first dose of 100  $\mu$ g and the second dose of 30  $\mu$ g, subjects initially received 100  $\mu$ g of vaccination will no longer receive the second vaccination. After the second vaccination, 8.3% (1/12) of subjects in 10  $\mu$ g group and 75.0% (9/12) of subjects in 30  $\mu$ g group got fever  $\geq$ 38.0° C. The fever usually got resolved within 1 day of onset. There was no systemic event or fever of grade 4. Most local reactions and systemic events peaked 2 days after vaccination and resolved at day 7.

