#### 10.1.2 Solicited reactions

The occurrence of selected indicators of safety will be measured/collected for 14 days after each vaccination (including the days of vaccine vaccination), see details in following **Table** 5.

Table 4 Solicited local and systemic reactions

Local reactions (vaccination site):	Pain/tenderness
	Erythema/redness
	Induration/swelling
Systemic reactions:	Fever (a)
	Nausea
	Vomiting
	Diarrhea

Headache
Fatigue
Myalgia
Arthralgia
Chills
Loss of appetite
Malaise

(a) Based on recorded body temperature, fever is defined as axillary temperature ≥37.3°C.

The intensity of solicited safety parameters will be assessed respectively as described in grading scale of Appendix B and C.

Solicitation adverse reactions: there is at least a reasonable possibility of a causal relationship between vaccines and adverse events, that is, causality cannot be ruled out.

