# 10.3 Assessment of safety parameters

# 10.3.1 Assessment of intensity

Reaction signs and symptoms involved in the grading scale will be graded respectively by the investigator according to the Guidelines for Adverse Event Classification Standards for Clinical

Trials of Preventive Vaccines of NMPA (Appendix B) and FDA (Appendix C). AEs uninvolved in the grading scale will be graded clinically by the investigator according to following criteria. Grading and seriousness need to be assessed independently for each AE recorded on the CRF.

Mild	Grade 1	Lasting for a short time (<48h) or slight discomfort, which do not influence activity and no treatment is needed.
Moderate	Grade 2	Mild or moderate limitation of activity, which may require hospital visit, does not require or only requires mild treatment.
Severe	Grade 3	Obvious limitation of activity, which requires hospital visit and treatment, possibly requires hospitalization.
Critical	Grade 4	Possibly life-threatening; serious limitation of activity, which requires intensive care
Death	Grade 5	

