Appendix B. Table 2 Grading scale for vital signs

Signs	Grade 1	Grade 2	Grade 3	Grade 4
Fever* [Axillary temperature (°C)]	37.3~<38.0	38.0~<38.5	38.5~<39.5	≥39.5 for more than 3 days
ECG PR interval extension or atrioventricular block	PR interval 0.21 ~ <0.25 seconds	PR interval ≥0.25 seconds or second- degree atrioventricular block type I	Second-degree atrioventricular block type II or ventricular interval ≥ 3 seconds	Complete atrioventricular block
Signs	Grade 1	Grade 2	Grade 3	Grade 4
Heart rate				
Tachycardia (beats/minute)	101~115	116~130	>130	Arrhythmia requiring emergency treatment or hospitalization
Bradycardia (beats/minute)	50~54	45~49	<45	Arrhythmia requiring emergency treatment or hospitalization
Blood pressure				
Hypertension (mmHg)	Systolic blood pressure: 140 ~ <160 or diastolic blood pressure: 90 ~ <100	Systolic blood pressure: ≥160 ~<180 or diastolic blood pressure: ≥100 ~<110	Systolic blood pressure: ≥180 or diastolic blood pressure: ≥110	Occurrence of previously undiagnosed life-threatening complications (eg malignant hypertension) or hospitalization
Hypotension (systolic blood pressure) (mmHg)	85~<89	80~<85	<80	Shock or hospitalization
Respirator rate (times/minute)	17~20	21~25	>25	Intubation required

\*\* The maximum measured diameter or area should be used.

Note: \* Axillary temperature is usually adopted in China, and it can be converted into oral temperature and anal temperature if necessary. Generally, oral temperature = axillary temperature + 0.2 °C;

Anal temperature = axillary temperature +  $(0.3 \sim 0.5^{\circ}\text{C})$ . When persistent high fever occurs, the cause of high fever should be identified as soon as possible.

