Appendix B. Table 3 Grading scale for non-vaccination site (systemic) reactions

Organ system symptoms/signs	Grade 1 Grade 2		Grade 3	Grade 4		
Gastrointestinal system						
Diarrhea	Mild or transient, 3 to 4 times/day, abnormal fecal appearance, or mild diarrhea lasting less than 1 week	Moderate or persistent, 5-7 times/day, abnormal fecal appearance, or diarrhea> 1 week	>7 times/day, abnormal fecal appearance, or hemorrhagic diarrhea, orthostatic hypotension, electrolyte imbalance, needing intravenous infusion> 2L	Hypotension shock, needing hospitalization		
Constipation*	Stool softener and diet adjustment needed	Laxative medications needed	Stubborn constipation requiring manual defaecation or enema	Toxic megacolon or intestinal obstruction		
Dysphagia	Mild discomfort when swallowing	Restricted diet	Diet and conversation are very limited; cannot eat solid food	Cannot eat liquid food; intravenous nutrition needed		
Anorexia	Loss of appetite, food intake not reduced	Loss of appetite, reduced food intake, but no significant weight loss	Loss of appetite and significant weight loss	(Such as gastrointestinal feeding, parenteral nutrition)		
Vomiting	1 ~ 2 times/24 hours without affecting activities	3 ~ 5 times/24 hours or limited activity	> 6 times within 24 hours or intravenous fluid therapy needed	Due to hypotensive shock, hospitalization or other means of nutrition are required		
Transient (<24 hours)  or intermittent with basically normal food intake		Persistent nausea leading to reduced food intake (24 to 48 hours)	Persistent nausea leading to almost no food intake (> 48 hours) or the need for intravenous fluid therapy	Life threatening (Such as hypotension shock)		
Musculoskeletal ar	nd connective tis	sue				

Organ system symptoms/signs	Grade 1	Grade 2	Grade 3	Grade 4
Myalgia (Non-vaccination site)	Do not affect daily activities	Slightly affect daily activities	Severe muscle pain, severely affecting daily activities	Emergency treatment or hospitalization
Arthritis	Mild pain, accompanied by inflammation, erythema, or joint swelling; but not hindering function	Moderate pain, accompanied by inflammation, erythema, or joint swelling; hindering function, but not affecting daily activities	Severe pain, accompanied by inflammation, erythema, or joint swelling; affecting daily activities	Permanent and/or disabling joint damage

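### The SAP reads a blank NMPA grade as too mild to count, but the NMPA fever row has no grade for axillary fever of 39.5 °C or more lasting 3 days or less

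*SAP*

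**What the plan says.** SAP 7.1.2, in the paragraphs on severity of related TEAEs, sets a two-way rule for the two grading scales. The direction that matters here begins "if the severity of related TEAE under FDA Guidance is at least grade 1" and continues "which under China NMPA Guidance is less than grade 1 (ie. NULL in EDC), the corresponding event will not be regarded as adverse event", with the exclusion applying under the NMPA guidance. The parenthesis ties being below Grade 1 to one database state, an empty grade field.

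Protocol Appendix B Table 2 grades axillary fever as 37.3 to <38.0 °C (Grade 1), 38.0 to <38.5 °C (Grade 2) and 38.5 to <39.5 °C (Grade 3). Grade 4 is "≥39.5 for more than 3 days". Only Grade 4 carries a duration condition.

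Protocol Appendix C Table 3 (FDA) grades fever from 38.0 °C, with Grade 3 at 39.0 to 40.0 °C and Grade 4 above 40.0 °C. It has no duration condition and is defined on oral temperature. The note to Appendix B Table 2 gives the conversion: "oral temperature = axillary temperature + 0.2 °C".

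Protocol 10.1.2 sets the trial's own threshold: "fever is defined as axillary temperature ≥37.3°C".

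Protocol 10.3.1 offers a fallback, but a limited one: "AEs uninvolved in the grading scale will be graded clinically by the investigator according to following criteria".

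**The concern.** A blank grade can mean two different things: the event is below the scale's lowest grade, or the scale has no category for it. The SAP rule recognises only the first. Under Appendix B, a fever of 39.5 °C or more that resolves within 3 days is of the second kind, and it sits at the top of the scale.

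Fever is a solicited systemic reaction, and solicited systemic reactions are a primary endpoint. SAP 7.6.1 uses NMPA as the only scale for the general Grade ≥3 TEAE and related-TEAE tables. An error here would remove the hottest short fevers and keep cooler ones, so NMPA-based reactogenicity would be understated. The duration condition is no remote technicality: of the earlier US study of this vaccine, Protocol 4.2.4.1 says "The fever usually got resolved within 1 day of onset".

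**Working it through.** **Denominator.** The one computed design figure in the plan is the 86.5% chance of at least one TEAE among 24 subjects at a true rate of 8% (Protocol 13.3, SAP 4.3). 1 − 0.92^24 = 0.865, so it reproduces. This point does not depend on it, but uses the same 24 subjects per dose group per age group.

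**Step 1: map temperatures through both scales.** Axillary values in 0.1 °C steps were graded under Appendix B Table 2 for durations of 1 to 4 days, and under Appendix C Table 3 with and without the +0.2 °C conversion. Selected rows:

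| Axillary peak (°C) | NMPA, 1 to 3 days | NMPA, 4 days | FDA, +0.2 °C | FDA, no conversion |
|---|---|---|---|---|
| 37.2 | below 1 | below 1 | below 1 | below 1 |
| 37.3 | 1 | 1 | below 1 | below 1 |
| 37.8 | 1 | 1 | 1 | below 1 |
| 38.0 | 2 | 2 | 1 | 1 |
| 38.5 | 3 | 3 | 2 | 2 |
| 39.4 | 3 | 3 | 3 | 3 |
| 39.5 | none | 4 | 3 | 3 |
| 39.8 | none | 4 | 3 | 3 |
| 39.9 | none | 4 | 4 | 3 |
| 40.1 | none | 4 | 4 | 4 |

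At 1, 2 or 3 days every value from 39.5 °C upward is ungraded under NMPA, and every one is FDA Grade 3 or 4. All therefore meet the rule's FDA condition.

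**Step 2: can the branch ever act correctly for fever?** It needs FDA Grade 1 or more and NMPA below Grade 1. FDA Grade 1 starts at 38.0 °C oral, which is 38.0 − 0.2 = 37.8 °C axillary, or 38.0 °C if no conversion is made. Both exceed the NMPA threshold of 37.3 °C. No temperature satisfies both conditions, so an empty NMPA grade beside an FDA fever grade means either the gap or a missing entry.

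**Step 3: does other text close the gap?**
- The 10.3.1 fallback is for events outside the scale; fever is in it.
- The instruction in Appendix B Table 1 to take the higher index concerns induration, swelling, rash and blush only.
- SAP 7.9 says missing data will not be handled.
- Protocol 12.1 does not allow blank eCRF items, which sits uneasily with a SAP that gives a blank a meaning.

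**Step 4: size.** Each subject lost removes 1/24 = 4.17 percentage points of NMPA fever incidence in a dose group, or 1/48 = 2.08 points with the age groups pooled (SAP 7.8). Two subjects in one group are 2/24 = 8.33 points.

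The documents give no rate for fevers of this kind. Under assumed true rates p, the chance of at least one in 24 is 1 − (1 − p)^24:

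| Assumed p | Chance of at least one in 24 |
|---|---|
| 1% | 21% |
| 2% | 38% |
| 5% | 71% |
| 10% | 92% |

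These are chances that such a fever occurs, not that it is removed.

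**The case against.** The strongest reply is that the operative test is being below Grade 1, with the blank only describing how that state is stored. On that reading a 39.6 °C fever is plainly not below Grade 1, and removal needs two lapses: a site leaves the grade empty, and a programmer reads the blank literally. Protocol 10.2.2 has the investigator judge severity, 12.1 forbids blanks, 12.2 requires issues to be resolved before lock, and 13.1 adds a blinded data review. This makes removal less likely. It does not answer the point, because no text tells the investigator which grade to enter, and the SAP equates the blank with mildness in so many words.

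Several stronger readings are tempting, and the documents do not support them:

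- *Every short fever of 39.5 °C or more is lost.* No. The grade must be blank and the event related, and a subject with another diary day at 37.3 to 39.4 °C has a gradable value.
- *The loss is 4.2 points of Grade ≥3 fever.* That presumes the missing grade. Only overall NMPA fever incidence can be quantified.
- *The signal disappears.* SAP 7.6.1 also grades related systemic reactions on the FDA scale, with its own Grade ≥3 table, and lists related TEAEs by subject. The DLT criterion for fever above 40.0 °C does not use the grade. The any-TEAE and related-TEAE tables name no scale, so removal from them is inference.
- *Such fevers will be common, because 75% of the US 30 µg group had fever after dose 2.* That figure is for 38.0 °C or more. The same section reports no Grade 4 fever and one Grade 3 fever at 30 µg.
- *Vomiting has the same hole.* Barely. Grade 2 ends at 5 episodes and Grade 3 starts at "> 6 times within 24 hours", but limited activity or intravenous fluids also assign a grade. Only exactly six episodes with neither are ungraded.

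**Conclusion.** The concern holds in a limited form. For fever, the branch that excludes events with an FDA grade and a blank NMPA grade cannot identify a fever too mild to count; it can only remove one wrongly. The error runs in the anti-conservative direction on a primary safety endpoint, and it inverts the ordering: a one-day 39.4 °C fever is kept as NMPA Grade 3, while a one-day 39.5 °C fever stored as blank is dropped.

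The size is 4.2 percentage points of NMPA fever incidence per subject lost in a group of 24. This rests on three conditions: the fever is judged related, its NMPA grade is left blank, and its only recorded febrile values are 39.5 °C or more over 3 days or less. How often they coincide cannot be derived from the documents, and any effect on Grade ≥3 counts depends on the grade assigned. It should be corrected, but it does not threaten the trial's ability to detect high fever.

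**What to change.** Reword SAP 7.1.2 so that an event is excluded under a scale only when its recorded value or description is shown to lie below that scale's Grade 1 cut-off. Any other blank grade is queried before database lock; if it stays unresolved, the event remains in the incidence tables under a separate category for grade not assigned. Below Grade 1 and no grade defined should have different codes.

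The sponsor should reconcile the Appendix B fever row with the SAP rule, and record the outcome, before unblinding. Appendix B reproduces national guidance, so this can be a documented convention that leaves its cut-offs unchanged. Which grade applies is for the sponsor to settle. The six-episode vomiting case can be noted at the same time.

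The cost is a few lines of SAP text, one edit check comparing temperature with grade, and a small number of queries. No new data are needed.
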